9.1.4. Optional Screening - Open-Label Extension

For the open-label extension period, the optional screening visit should take place no later than 21 days after the subject has been offered the opportunity to enter open-label extension period and in any event must occur within 14 days prior to Week 104.

9.1.5. Open-Label Extension Period

Subjects meeting the inclusion criteria applicable for responders and who are willing to participate will restart active study treatment in the open-label extension period.

9.1.5.1. Active Treatment Period: OL Weeks 0 To 52

Restart: OL Week 0

Restart will occur no later than 14 days after screening is initiated and will be designated as Week 0 and Day 1 of the study. In no event can a subject be restarted if they have completed the Week 104 visit. At this visit, inclusion and exclusion criteria, concomitant medications, and laboratory evaluations should be reviewed and documented to determine that a subject remains

eligible for participation in the study. All paper diary data collected since screening will be reviewed by clinic staff. Subjects should have at least 10 days of daily insulin use immediately preceding restart. Subjects will be restarted to receive golimumab as described in Section 3.1. Subject weight and height will be obtained to determine dose and device.

The dose of study agent (golimumab) will be administered at the study site. Subjects should be monitored for at least 30 minutes following injection and be observed for any adverse reactions, including injection site reactions (See Section 9.9). Subjects/caregivers who want to participate in study agent “self-administration” outside of some study visits begin training on using the sponsor-supplied single-use injection devices (See details Section 6.2). Additional training on the paper diary and glucometer will be given as needed.

Future target dosing and study visit days will be calculated based on the day of initial dosing (Week 0) and will not be redefined later during the study. Therefore, the study staff are encouraged to discuss the study visit days with subjects/caregivers and consider this schedule to determine what might be the anticipated (ie, day of the week) for future dosing and study visits. Specific study visits and study agent treatment windows and impact on study compliance is detailed in Section 7.

At this visit, subjects/caregivers will be supplied with a calendar with target dosing days and target study visit days that show dosing and visit windows (See Section 7.1.2.1).

Study Visits: OL Weeks 2 and 4

A PK sample will be drawn at visits in OL Weeks 0, 4, 12, 28, and 52. Subjects/caregivers who are participating in administering injections are to return used devices and receive additional injection devices and supplies, if needed, at these visits. The visit windows for these study visits are ± 3 days from the target dosing (visit) day except for OL Week 0.

9.1.5.2. Study Agent Self-Administration or Dosing-Only Visits: OL Weeks 0, 2, 4, 12, 20, 28, 36, 44, and 50

After OL Week 4, subjects/caregivers who have met the training requirement, are given the option to self-administer majority of the study agent doses off-site that do not coincide with study visits. As detailed in Section 6.2 and the IFU, subjects/caregivers will receive training on administration during the first 3 dosing visits, and at study visits preceding off-site administration subjects will receive the appropriate study agent devices for dosing until the next dosing visit as well as supplies and instructions on handling and storage before and after usage. Subjects/caregivers will enter information including date and time of dosing, device used, anatomic site injected, and person administering dose into their paper diary. Subjects/caregivers will be asked to closely monitor the study agent injection site for at least 30 minutes and intermittently thereafter. During self-administration, subjects/caregivers are to contact the study-site team in the event of problems or complication including but not limited to signs of immediate or delayed local or systemic reaction (Section 9.9). These dose administrations should occur ± 3 day of target dosing day as detailed above.

For subjects/caregivers unwilling or unable to administer the injection, subjects/caregivers are to work with the site team to develop a visit schedule to meet the dosing criteria in Section 9.1.5 and per the [Time and Events Schedule](#). These study agent dosing-only visits are to take place ± 3 days of the target dosing day except for OL Weeks 0 and 2.

9.1.5.3. Post-Treatment Visit

The last dose of study agent is to be administered at the Week 50. A post-treatment visit will be conducted for all subjects at OL Week 60 or 10 weeks after the last dose of study agent to collect SAEs and AEs of interest since the last visit unless the subject has died, has been lost to follow-up, or has withdrawn consent. If a study visit is not possible, follow-up information may be collected via email or other electronic means.

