Clinical Assessments / Ongoing Review											
Full Physical examination	X									X	X
Brief physical examination		X	X	X	X	X	X	X	X		
Vital signs	X	X	X	X	X	X	X	X	X	X	X
Height & Body weight measurement		X			X		X		X		X
Interval history and paper diary review		X	X	X	X	X	X	X	X	X	
Previous/concomitant medication review	X	X	X	X	X	X	X	X	X	X	X
IDAA1c	X	X	X	X	X	X	X	X	X	X	
Adverse events	X	X	X	X	X	X	X	X	X	X	X
Tuberculosis (TB) exposure review	X	X	X	X	X	X	X	X	X	X	X
Randomization and Study Agent Administration											
Dose determination and modification		X			X		X		X		
Required study agent administration at study site ^f		X	X	X	X	X	X	X	X		
Subjects participating in self-administration^b											
Injection training by site personnel ^b		X									

Open-Label Extension Period											
Study Designation	Screening ^q	Active Treatment ^{b,c}									Post-Treatment ^d
Study Week ^a		OL 0	OL 2	OL 4	OL 12	OL 20	OL 28	OL 36	OL 44	OL 52 (EOSV) ⁿ	OL 60 or 10 weeks post last dose
Study Day ^a (visit window in days)	-14 to -1	1	15 (±1)	29 (±3)	85 (±3)	141 (±3)	197 (±3)	253 (±3)	309 (±3)	365 (±3)	421 (±7)
Study Procedure											
Distribute study agent injection devices				X	X	X	X	X	X		
Return study agent injection devices					X	X	X	X	X	X	
Subject Reported Data / Paper Review											
Insulin use report review	X	X	X	X	X	X	X	X	X	X	
Hypoglycemia event review		X	X	X	X	X	X	X	X	X	X
Study agent self-administration review ^b				X	X	X	X	X	X	X	
Clinical Laboratory Assessments											
4h - Mixed-meal tolerance test (MMTT) ^g	X						X			X	
HbA1c	X	X	X	X	X	X	X	X	X	X	X
QuantiFERON-Gold test	X										
Serum pregnancy test ^h	X										
Urine pregnancy test ^h		X	X	X	X	X	X	X	X	X	X
Hematology ⁱ	X	X	X	X	X	X	X	X	X	X	X
Chemistry ⁱ	X	X	X	X	X	X	X	X	X	X	X
Viral serology ^j	X										
Polymerase chain reaction (PCR) Viral load ^k	X				X			X		X	
Clinical Pharmacology											
Golimumab concentration ^l		X	X	X	X	X	X	X	X	X	
Antibodies to golimumab ^l		X	X	X	X	X	X	X	X	X	X
Free/total TNF α ^l		X	X	X	X	X	X	X	X	X	X
Biomarkers and Pharmacogenomics^o											
Peripheral blood mononuclear cell (PBMC) sample collection ^m	X									X	
Serum biomarker sample ^m		X								X	

Abbreviations: EOSV=End of Study Visit, ICF=informed consent, IDAA1c=insulin dose-adjusted HbA1c, MHC=major histocompatibility complex, MMTT=mixed-meal tolerance test, OL=open-label, PBMC=peripheral blood mononuclear cell, PCR=polymerase chain reaction, TB=tuberculosis, TNF α =tumor necrosis factor alpha

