- a. The study visit Week and target study visit Day are indicated and calculated based on the day of first dose. Acceptable windows for study visits in days before (-) or after (+) target study visit day are indicated and based on if study agent dosing will be given at that visit and time enrolled in the study.
- b. Subjects/caregivers will be given the option for at home “self-administration” for study agent doses after OL Week 4, since the dosing schedule for subject is q2w through OL Week 50. Training on self-administration will be provided at OL Week 0 (See Section 6.2 for details). These subjects will record data regarding self-administration in the paper diary (See Section 7.1.1.1) or if self-administering at the site, the data will be recorded in the study site’s documents, not in the paper diary.
- c. Subjects not participating in self-administration will schedule study agent dosing-only visits every 2 weeks through OL Week 50 (see Section 9.1.39.1.5).
- d. The post-treatment visit will be conducted for all subjects at OL Week 60 or 10 weeks after the last dose of study agent to collect SAEs and AEs of interest since the last visit unless the subject has died, has been lost to follow-up, or has withdrawn consent.
- e. For those who do not meet study criteria or choose not to participate in this study, instructions on how to return the paper diary will be given.
- f. This does not represent all study agent dosings. At OL Weeks 0, 2, and 4, administration will occur during study visits. At OL Weeks 12, 20, 28, 36, 44, and 50 study visits where study agent will be administered, either subjects/caregivers or study staff may administer the injection. At the required visits in this table, drawing of pharmacokinetic/immunogenicity (ie, golimumab concentration and antibodies to golimumab) samples must take place **prior** to study agent administration at visits where study agent dosing occurs. Following study agent administration subjects will be observed for 30 minutes for symptoms of injection reactions. The last dose of study agent is to be administered at Week 50. See Section 6.1 and Section 9.1.5.3.
- g. The MMTT will be a 4-hour assessment to be conducted in the morning after an overnight fast. All other blood samples should be drawn prior to the MMTT. When MMTT occurs on study agent dosing days, study agent should be administered after the MMTT.

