9.2.3.1. Safety Endpoints – Open-Label Extension Period

[figure not shown]
- Proportion of subjects with treatment-emergent AEs and severe AEs through OL Weeks 52 and 60.
- Proportion of subjects with study agent injection site reactions through OL Week 52.
- Proportion of subjects with severe infections through OL Weeks 52 and 60.

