10. SUBJECT COMPLETION/DISCONTINUATION OF STUDY TREATMENT/ WITHDRAWAL FROM THE STUDY

10.1. Completion

A subject will be considered to have completed the study if he or she has completed assessments at Week 104 of the off-therapy follow-up period or Week 60 of the open-label extension period of the study.

Subjects who prematurely terminate study participation for any reason before completion of the study will not be considered to have completed the study. Subjects are able to initiate the prohibited medicines and activities per the guidance provided in Section 4.3 and Section 8.3.

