12.4. Procedures

12.4.1. All Adverse Events

All AEs and special reporting situations, whether serious or non-serious, will be reported from the time a signed and dated ICF is obtained until completion of the subject's last study-related procedure, which may include contact for follow-up of safety. Serious adverse events, including those spontaneously reported to the investigator within 52 weeks after the last dose of study agent (which is the end of the study), must be reported using the Serious Adverse Event Form. In

addition, SAEs will be requested to be submitted for subjects who withdraw early from the study for a year after their last study agent dose. The sponsor will evaluate any safety information that is spontaneously reported by an investigator beyond the time frame specified in the protocol.

All events that meet the definition of an SAE will be reported as SAEs, regardless of whether they are protocol-specific assessments. Anticipated events will be recorded and reported as described in [Attachment 6](#).

All AEs, regardless of seriousness, severity, or presumed relationship to study agent or device, must be recorded using medical terminology in the source document and the CRF. Whenever possible, diagnoses should be given when signs and symptoms are due to a common etiology (eg, cough, runny nose, sneezing, sore throat, and head congestion should be reported as "upper respiratory infection"). Investigators must record in the CRF their opinion concerning the relationship of the AE to study therapy. All measures required for AE management must be recorded in the source document and reported according to sponsor instructions.

All devices associated with device-related AEs will be investigated including the return of the device to the sponsor for inspection.

The sponsor assumes responsibility for appropriate reporting of AEs to the regulatory authorities. The sponsor will also report to the investigator (and the head of the investigational institute where required) all suspected unexpected serious adverse reactions (SUSARs). The investigator (or sponsor where required) must report SUSARs to the appropriate Independent Ethics Committee/Institutional Review Board (IEC/IRB) that approved the protocol unless otherwise required and documented by the IEC/IRB. A SUSAR will be reported to regulatory authorities unblinded. Participating investigators and IEC/IRB will receive a blinded SUSAR summary, unless otherwise specified.

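### The protocol contradicts itself on which adverse events are collected at the OL Week 60 visit, and its 52-week SAE wording was not adapted to the open-label extension

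*Protocol*

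**What the plan says.** **Which events are collected.** Protocol 9.1.5.3 places the post-treatment visit at OL Week 60 or "10 weeks after the last dose of study agent to collect SAEs and AEs of interest since the last visit". Footnote d of the open-label Time and Events Schedule gives the same purpose: "to collect SAEs and AEs of interest since the last visit unless the subject has died". Neither passage defines AEs of interest.

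The extension's safety endpoints in 9.2.3.1 include "Proportion of subjects with treatment-emergent AEs and severe AEs through OL Weeks 52 and 60", and severe infections through the same two timepoints. Section 12.4.1 requires every AE, serious or not, from consent until the subject's last study procedure, and says that this procedure can be a safety follow-up contact. Section 9.6.1, which is specific to the extension, has AEs reported throughout the study. In the open-label schedule the general adverse-event row is marked in every column, including OL Week 60.

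**How long SAEs are covered.** Section 12.4.1 requires SAE reports, including spontaneous ones, "within 52 weeks after the last dose of study agent (which is the end of the study". It adds that "SAEs will be requested to be submitted for subjects who withdraw early from the study for a year after their last study agent dose". Section 12.4.2 treats deaths within 52 weeks of the last dose as SAEs. For the extension, 9.1.5.3 states "The last dose of study agent is to be administered at the Week 50", and 10.1 counts a subject as complete at "Week 60 of the open-label extension period of the study".

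The SAP is limited to the Week 52 database lock and settles neither matter.

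**The concern.** Safety is a stated part of the extension's objective, in young subjects who are re-exposed to a TNF blocker. A site preparing for the OL Week 60 visit will probably read the section that describes that visit, and that section is narrower than the endpoint the visit feeds. Sites could reasonably collect different things over OL Weeks 52 to 60, which is the only interval separating the two endpoint timepoints.

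The undefined term makes this worse. Protocol 12.4.4 lists malignancy, opportunistic infection and TB as events of special interest. SAP 6.1, written for the Week 52 lock, gives hypoglycemia, infections, TB and malignancy as examples. A severe but non-serious ordinary infection falls outside the first list and inside the second, yet 9.2.3.1 counts it.

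On duration, the parenthesis in 12.4.1 appears to have been carried over from the double-blind design. In the extension, early withdrawers are covered by an explicit one-year SAE request, while subjects who take every dose and complete are not. If subjects withdrawn under 10.2 for a worsening remission score count as early withdrawers, the request would also depend on the efficacy outcome.

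**Working it through.** This is a comparison of passages plus calendar arithmetic, using the schedule's convention Day = 7 × week + 1.

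**1. Reproduce the stated timing.** Last extension dose at OL Week 50: 7 × 50 + 1 = Day 351. Ten weeks later: 351 + 70 = Day 421. OL Week 60: 7 × 60 + 1 = Day 421. This matches the schedule's column, "OL 60 or 10 weeks post last dose", Day 421 (±7). The visit window gives (414 − 351)/7 = 9 to (428 − 351)/7 = 11 weeks after the last dose.

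**2. Compare the instructions for OL Week 60.**

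| Place in the protocol | AE scope at OL Week 60 |
|---|---|
| 9.1.5.3 | SAEs and AEs of interest |
| Open-label schedule, footnote d | SAEs and AEs of interest |
| Open-label schedule, adverse-event row | AEs, no restriction in the row |
| 9.6.1 | AEs for the study's duration |
| 12.4.1 | All AEs, serious or not, to the last procedure |
| 9.2.3.1 (endpoint) | Treatment-emergent AEs, severe AEs, severe infections |

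SAEs are in scope on every reading. The conflict concerns non-serious events that are not of interest, some of which may be severe.

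**3. Interval at risk on the narrower reading.** OL Week 52 is Day 365. 421 − 365 = 56 days = 8 weeks, and 8/60 = 13% of the OL Week 60 endpoint window. This is a share of time, not of events.

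**4. SAE window.**
- Double-blind: last dose Week 52 (Day 365), end Week 104 (Day 729). 729 − 365 = 364 days = 52 weeks, so the parenthesis in 12.4.1 is correct.
- Extension: 351 + 364 = Day 715 = OL Week 102. Completion is at OL Week 60, and 102 − 60 = 42 weeks, or 42/52 = 81% of the window, follow the last scheduled contact. With the ±7-day visit window this is 41 to 43 weeks.

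**5. Dependence on the last-dose week.** Section 9.1.5.1 lists OL Week 52 among the dosing visits and 7.1.1.1 states 27 extension doses, whereas two-weekly dosing from OL Week 0 to OL Week 50 gives 50/2 + 1 = 26. Those passages must be reconciled. If the last dose were at OL Week 52, ten weeks later would be OL Week 62 and the 52-week window would end at OL Week 104. The uncovered part would be 104 − 62 = 42 weeks, or 104 − 60 = 44 if the visit stayed at OL Week 60. The conclusion does not depend on which is right.

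**The case against.** The strongest reply is that the visit text states a purpose and not a limit. It never says that other AEs are to be left out. Sections 12.4.1 and 9.6.1 and the schedule row all call for full collection, and the OL Week 60 column also has a full physical examination, vital signs, hematology, chemistry, and concomitant-medication, hypoglycemia and TB review. A site following those passages would deliver the endpoint. This stands. A reader might infer that the visit collects only SAEs and AEs of interest, or that the endpoint cannot be delivered, but the documents support neither. They support a contradiction.

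A reader might also infer that the OL Week 60 proportions will be too low. That holds only if sites follow the narrower text and qualifying events occur in those 8 weeks. The OL Week 52 proportions are reported separately and are unaffected, and the extension is descriptive with no hypothesis tests.

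Protocol 11.9 could be read as ending treatment emergence with the treatment period, which would leave little to count after the last dose. But 9.2.3.1 names OL Week 60 for these endpoints, and the severe-infection endpoint carries no treatment-emergent qualifier.

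On duration, the SAE rule is a reporting duty that covers spontaneous reports and does not need a visit. Nothing exempts extension completers. It would be wrong to infer that their SAE follow-up is cancelled at OL Week 60; it becomes passive. The one-year arrangement for early withdrawers is a request for SAE reports, not a series of visits.

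Finally, the 90-day, 120-day, 6-month and 12-month intervals in 4.4 concern contraception, gamete donation and vaccination. They are not AE-collection windows and do not show that a 10-week visit is too early. That timing is a design choice.

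**Conclusion.** The concern holds as an internal contradiction with a practical consequence. Two passages describe a narrower collection at OL Week 60 than the endpoint needs and than three other passages require. If sites follow the narrower text, non-serious AEs not of interest with onset in the last 8 of 60 weeks may be missed, and the OL Week 60 figures would combine complete collection to OL Week 52 with partial collection afterwards. How many events this affects cannot be derived from the documents, which give neither the number entering the extension nor expected event rates.

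Separately, the 12.4.1 parenthesis is right for the double-blind period and wrong for the extension. For completers, 42 of the 52 weeks after the last dose carry no scheduled contact or stated request, while the duty to report remains.

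The figures assume a last dose at OL Week 50 and the visit on its target day. Neither issue touches the primary analysis or any hypothesis test. Both should be corrected because the extension's safety summaries rest on this wording.

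**What to change.** 1. In 9.1.5.3 and open-label footnote d, have the OL Week 60 visit collect all AEs, in line with 9.2.3.1 and 12.4.1. If AEs of interest is kept for any other purpose, define it.
2. In 12.4.1, limit the parenthesis to the double-blind period and state how the 52-week SAE window applies to subjects who complete the extension. Applying the existing one-year SAE request to them is one option. Adding scheduled contacts over that year would be a design preference and is not needed to resolve the contradiction.
3. Reconcile the passages on the last extension dose and the dose count, since the 10-week and 52-week points are measured from it.

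The cost is protocol wording and a full AE page at a visit already scheduled. If the one-year request is extended to completers, SAE reports will continue to be handled after OL Week 60.

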9.1.6. All Study Visits - Early Detection of Active Tuberculosis

To aid in the early detection of TB reactivation or new TB infection during study participation, subjects must be evaluated for signs and symptoms of active TB at scheduled visits (refer to the [Time and Events Schedule](#)). The following series of questions is suggested for use during the evaluation and should be addressed at all study visits:

- “Have you/Has your child had a new cough of >14 days’ duration or a change in a chronic cough?”
- “Have you/Has your child had any of the following symptoms:
 - Persistent fever?
 - Unintentional weight loss?
 - Night sweats?”
- “Have you/Has your child had close contact with an individual with active TB?” (If there is uncertainty as to whether a contact should be considered “close,” a physician specializing in TB should be consulted.)

If the evaluation raises suspicion that a subject may have TB reactivation or new TB infection, an immediate and thorough investigation should be undertaken, including, where possible, consultation with a physician specializing in TB.

Investigators should be aware that TB reactivation in immunocompromised subjects may present as disseminated disease or with extrapulmonary features. Subjects with evidence of active TB should be referred for appropriate treatment.

Subjects who experience close contact with an individual with active TB during the conduct of the study must have a chest radiograph, a repeat QuantiFERON-TB Gold test and, if possible, referral to a physician specializing in TB to determine the subject’s risk of developing active TB and whether treatment for latent TB is warranted. Study agent administration should be interrupted during the investigation. If the QuantiFERON-TB Gold test result is indeterminate, the test should be repeated as outlined in Section 9.1.2 and Section 9.1.2.1. Subjects should be encouraged to return for all subsequent scheduled study visits according to the protocol.

